### 6.1.8 Quality of life

#### Cushing QoL questionnaire

Completion of nine or more items of the 12-item Cushing QoL questionnaire is required for it to be considered evaluable for that assessment. If there are more than 3 items missing at an assessment, the total score will be set to missing (i.e., no more than 25% missing items). Standardized scores are calculated as follows:

First raw scores are obtained as the sum of the ratings on all QoL questions for a single patient. Table 6-4 shows the ratings for each answer of the QoL questionnaire.

**Table 6-4 Cushing QoL Questionnaire ratings**

Answers to HRQoL questions	Rating
'Always' or 'Very much'	1
'Often' or 'Quite a bit'	2
'Sometimes' or 'Somewhat'	3
'Rarely' or 'Very little'	4
'Never' or 'Not at all'	5

Then the standardized score,  $Y$ , is calculated for each patient as  $Y = 100 * (X - n)/(n*5 - n*1) = 100 * (X - n)/4*n$

where  $X$  denotes the raw score and  $n$  the number of questions answered by the patient.

The higher the score, the better the QoL. The best possible standardized score is 100, and the worst possible standardized score is 0.

### EQ-5D Health Questionnaire

The EQ-5D-3L consists of 2 pages – the EQ-5D-3L descriptive system and the EQ visual analogue scale. The descriptive system comprises the same 5 dimensions as the EQ-5D-3L (mobility, self care, usual activities, pain/discomfort, anxiety/depression). However, each dimension now has 3 levels: no problems, some problems and problems.

Health state classification will be converted to utility scores, during data analysis stage, based on a list representing the EQ-5D value set for the UK using the time trade-off method. This list has 243 values for all possible EuroQoL health states. For example, a health state of 11111 will have a score of 1.00 and a health status of 12132 will have a score of 0.089. If at least one of the five items is missing, the utility score will be set to missing.

The list representing the EQ-5D value set for the UK is based on a regression model and the following worked example indicates how these coefficients are to be used so as to compute the estimated values for each state (Table 6-5).

**Table 6-5 EQ-5D preference weight scoring system**

EuroQoL dimension	Level 2	Level 3
Mobility	0.069	0.314
Self-care	0.104	0.214
Usual activity	0.036	0.094
Pain / discomfort	0.123	0.386
Anxiety / depression	0.071	0.236
	Constant = 0.081 subtract for any state different from (1 1 1)	N3 = 0.269 subtract for any state with at least one level 3

The arithmetic needed to recover the estimated value for any health state from this table of decrements is given by the following example:

- Taking health state 1 1 2 2 3
- Full health ( 1 1 1 1 1 ) = 1.0
- Constant term (for any dysfunctional state)(subtract 0.081)
- Mobility.. level 1(subtract 0)
- Self-care.. level 1(subtract 0)
- Usual activity.. level 2(subtract 0.036)
- Pain / discomfort.. level 2(subtract 0.123)
- Anxiety / depression.. level 3(subtract 0.236)

---

- Level 3 occurs within at least 1 dimension (subtract N3 parameter 0.269)
- Hence the estimated value for state 1 1 2 2 3 is given by
- $1.0 - 0.081 - 0.036 - 0.123 - 0.236 - 0.269 = .255$

The EQ VAS records the respondent's self-rated health on a 20 cm vertical, visual analogue scale with endpoints labeled 'the best health you can imagine' and 'the worst health you can imagine'. This information can be used as a quantitative measure of health as judged by the individual respondents.

## 6.2 *SAS procedures used for inferential analysis computation*

### 6.2.1 Exact Clopper-Pearson confidence limits for a proportion

The SAS® procedure PROC FREQ will be used to determine proportions and the associated exact Clopper-Pearson 95% CI. The following SAS code will be used:

```
PROC FREQ DATA=xxx;
<BY cohort;>
TABLES binvar /BINOMIAL OUT=prop; OUTPUT OUT=yyy BINOMIAL;
RUN;
```

Here 'cohort' denotes a classification variable which identifies the cohorts, and 'binvar' denotes the binary variable for which the proportion and CI is calculated. 'binvar' must be coded such that the relevant level is the lowest level because the confidence interval is only calculated for this level. Get \_BIN\_ (binomial proportion), XL\_BIN, and XU\_BIN (lower and upper limit of CI) from output dataset yyy, merge it with the relevant level from dataset prop, and compare \_BIN\_ and PERCENT (must be identical) to make sure that the correct level was selected.

### 6.2.2 Distribution-free confidence interval for median

The SAS® procedure PROC UNIVARIATE will be used to calculate distribution-free confidence intervals based on order statistics. The following SAS code will be used:

```
ODS OUTPUT Quantiles=quant;
PROC UNIVARIATE DATA=xxx CIPCTLDF;
<BY cohort;> VAR numvar RUN;
```

Here 'cohort' denotes a classification variable which identifies the cohorts, and 'numvar' denotes the numerical variable for which the CI is calculated. Among other variables, the output dataset quant includes estimates (variable ESTIMATE), and lower and upper confidence limits (variables LCUDISTF and UCUDISTF) for various quantiles including the median (QUANTILE ='50% Median').

### 6.2.3 Mixed model for repeated measures

The following SAS code will be used to fit the mixed model for repeated measures.

```
proc mixed;
  class patient window ;
  model outcome = window base /ddfm=kr;
  repeated window /patient = patient type=un;
  lsmeans window / cl;
run;
```

Here, `patient` denotes the patient identifier (e.g. SID1A), `window` the time window assigned, `outcome` the outcome variable (e.g. mean UFC), and `base` the corresponding baseline value.

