6.5.1.5 Handling of missing data

For the analysis of these efficacy endpoints, for missing values, Mixed Effects Repeated Measured Model will be employed to assess the longitudinal changes in efficacy parameters. In addition, sensitivity analyses will be performed to assess the robustness of the efficacy findings.

The imputation method as well as sensitivity analyses will be specified in the RAP.

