### 6.1.7 Time windows

There is no visit schedule and no planned assessment in this non-interventional study. Assessment related data are collected as they become available during the study period. Therefore assessments are assigned to time windows based on the study day on which the assessment is performed. For mean UFC, the sample day of the first urine sample included in the calculation of mean UFC will be used for assignment to time windows.

If there are multiple values within a time window, the assessment closest to the target day of the time window will be used, if not indicated otherwise. If two assessments are equally close (e.g. 7 days before and 7 days after target day), the later will be used.

Time windows will be assigned according to the window schema in Table 6-2 if assessments are expected more frequently than every 6 months. Otherwise the time windows in Table 6-3 will be applied (e.g., for tumor volume, variables related to patient reported outcome questionnaires, findings of gallbladder ultrasound).

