#### 8.2.1 Secondary efficacy endpoints

The secondary efficacy endpoints are as follows:

---

1. Proportion of patients with a mean UFC  $\leq$  ULN at 1, 3, 6, 12, 24 and 36 months after enrollment into the study.
2. The absolute and percentage change from baseline in biochemical measures of disease activity (mean UFC, serum cortisol, serum cortisol after dexamethasone, salivary cortisol, ACTH, fasting serum lipid profile (total cholesterol, HDL, LDL)) over time.
3. Proportion of patients achieving normalization of biochemical measures of disease activity (serum cortisol, serum cortisol after dexamethasone, salivary cortisol, ACTH) over time, where normalization refers to being within the upper and lower limit of normal ranges.
4. The absolute and percentage change from baseline in clinical signs and symptoms (blood pressure, body weight, body mass index, waist circumference) over time.
5. The proportion of patients with favorable shift from baseline in clinical symptoms of Cushing's disease over time.
6. The change from the last dose of pasireotide s.c. to 90 days after permanent discontinuation of pasireotide s.c. for patients who discontinue pasireotide s.c. prior to completing 3-year observation period. This change will be evaluated for all available continuous efficacy parameters.
7. The absolute and percentage change from baseline in tumor size over time.
8. The absolute and percentage change from baseline in patient reported outcome questionnaires (Cushing QoL and EURO QoL) over time.

All efficacy analyses will be done for all patients in the FAS and for the two cohorts. And all efficacy analyses except those under 5 will be done for the subgroup patients from German sites. Additionally, the efficacy analyses described under 1, 2, and 3 above will be repeated for the following subgroups of patients:

- Patients treated with monotherapy pasireotide s.c. throughout the study
- Patients treated with a combination of pasireotide s.c. with any other therapy for Cushing's disease throughout the study
- Patients who switched from monotherapy to combination therapy or vice versa at any time during the study

For all continuous efficacy variables (biochemical measures of disease activity, blood pressure, body weight, body mass index, waist circumference, tumor size), a Mixed Effects Repeated Measures Model will also be employed to assess the longitudinal changes in these variables.

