Except for the analysis of change from end of treatment to 90 days later, the efficacy analyses will only consider on-treatment values, defined as values assessed before end of treatment + 3 days.

All assessments will be assigned to time windows based on the study day on which the assessment was performed. If there are multiple values within a time window, the assessment closest to the target day of the time window will be used, if not indicated otherwise. Further details including the start and end days of the time windows are available in Appendix 16.1.9 of the CSR.

The continuous efficacy parameters will be also evaluated through a couple of sensitivity analyses: the first will be imputing the worst value at that time window in case of missing data and the second on the patients with the full set of values. The same Mixed Model will be employed for both the analyses.

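### The mixed model prints window levels rather than change from baseline, and leaves the baseline at which they are evaluated to a software default that weights patients by their number of records

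*SAP*

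**What the plan says.** SAP 6.2.3 gives the code. The model statement is "model outcome = window base /ddfm=kr", where the dependent variable is described as "the outcome variable (e.g. mean UFC), and" the baseline value enters as a covariate. The only output requested is "lsmeans window / cl". There is no reference value for baseline, no contrast and no change variable.

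The stated purpose is change. In SAP 8.2.1, for the continuous efficacy variables, "a Mixed Effects Repeated Measures Model will also be employed to assess the longitudinal changes in these variables". In Protocol 6.5.1.5, on missing data, a "Mixed Effects Repeated Measured Model will be employed to assess the longitudinal changes in efficacy parameters". The corresponding endpoints are changes, for example "The absolute and percentage change from baseline in biochemical measures of disease activity", with parallel wording for clinical signs and tumour size.

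Two features make the number of records per patient unequal. SAP 8.2.1 states that "the efficacy analyses will only consider on-treatment values, defined as values assessed before end of treatment + 3 days", and SAP 6.1.7 that "There is no visit schedule and no planned assessment in this non-interventional study".

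Outside the model, SAP 8.2.1.2, 8.2.1.4 and 8.2.1.6 summarise observed absolute and percentage change by window, with distribution-free 95% intervals for the median change. SAP 8.2.1 adds two sensitivity analyses with the same model: one imputes the worst value where data are missing, the other keeps only patients with a full set of values.

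**The concern.** There are two gaps between the purpose and the printed output.

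First, the model is the protocol's tool for missing efficacy values, yet it returns adjusted levels. The change tables use observed data with no model. As written, the SAP prints no change estimate that addresses missing data, and no mean change with a confidence interval.

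Second, an adjusted mean from a model with a continuous covariate depends on the covariate value at which it is evaluated. The SAP does not set that value. If the default is the mean over analysed records, a patient with nine windows counts nine times and a patient with one window counts once. A reader who wants the change must subtract a baseline, and the one at hand in the baseline table is averaged over patients. The two averages differ whenever patients who contribute more records have systematically different baselines.

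The same default would give the main model and its two sensitivity analyses different reference baselines, so part of any difference between their window means would have nothing to do with robustness.

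**Working it through.** **Inputs from the documents.** Additive model in window and baseline (SAP 6.2.3); nine post-baseline windows, Month 1 to Month 36, for the biochemical measures (SAP 8.2.1.2); 100 to 200 patients (SAP 8.1.2). The plan states no figure for this model, so there is nothing to reproduce.

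**Assumptions not in the documents.** LS means hold a continuous covariate at its mean over analysed records. The baseline SD, slope and discontinuation pattern are also assumed.

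**Formula.** The LS mean at window k is a_k + B × b_ref, where B is the baseline slope. Moving b_ref from the patient mean (b_pat) to the record mean (b_rec) shifts every window by

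B × (b_rec − b_pat), where b_rec − b_pat = corr(n, base) × CV(n) × SD(base)

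and n is the number of records per patient. The shift does not depend on k.

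**Hand example.** 50 patients have 9 records and baseline 4; 50 have 2 records and baseline 6.
- b_rec = (50×9×4 + 50×2×6) / (50×9 + 50×2) = 2400/550 = 4.36; b_pat = 5.00; difference −0.64.
- Formula check: corr = −1, CV = 3.5/5.5 = 0.64, SD = 1, which gives −0.64.
- With B = 0.5, every LS mean moves by 0.5 × (−0.64) = −0.32.

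**Level versus change.** With baseline as a covariate, modelling outcome or outcome − base is the same fit. The LS mean change equals the LS mean level minus b_ref, and because b_ref is treated as fixed the interval keeps its width. Switching to change with the default reference leaves an error of (B − 1) × (b_rec − b_pat). In the example this is (−0.5) × (−0.64) = +0.32, the opposite sign.

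**Sensitivity models in the same example.** If the worst-value analysis fills all nine windows for everyone, its reference is 5.00. The complete-case analysis keeps only the 9-record patients, so its reference is 4.00. Against 4.36 in the main model, the reference alone moves LS means by 0.5 × 0.64 = +0.32 and 0.5 × (−0.36) = −0.18.

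**Simulation.** N = 100, nine windows, unstructured covariance, maximum likelihood, 4 replicates per cell, baseline SD 1, fitted slope 0.44 to 0.60. Leaving risk per window is at the mean baseline. Shifts are in baseline SD units.

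| Log-odds of leaving per baseline SD | Risk 10% | Risk 20% | Risk 30% |
|---|---|---|---|
| 0 | +0.01 | −0.01 | −0.02 |
| 0.5 | −0.07 | −0.09 | −0.14 |
| 1.0 | −0.12 | −0.19 | −0.22 |

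Where leaving depends on baseline, these shifts are 0.8 to 1.9 times the standard error of the Month 9 LS mean (about 0.09 to 0.12 in those cells). They are identical across windows to rounding. Modelling change without fixing the reference leaves 0.08 to 0.26 SD in those same cells.

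**The case against.** The strongest reply is that little is at stake. The change is unprinted, not lost, since it follows by subtraction. An LS mean at a particular reference baseline is a valid estimate at that baseline, not a biased one. Longitudinal change can also be read as change between windows, and those contrasts are untouched. Within-patient change is already reported descriptively, the model is an addition to those tables, and the study is exploratory with no hypothesis tests. All of this stands, and it limits the point to an improvement of the output. It does not supply a model-based change or a stated reference baseline.

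A reader might go further and infer that the model overstates the fall in UFC, because patients with high baseline values leave early. The documents do not support that:
- Nothing links baseline to leaving. Lack of effect is only one of seven withdrawal categories in Protocol 3.4.1.1.
- Record counts can also push the other way. Protocol 3.5.3.1 expects the frequency of UFC testing to change once control is reached, with a six-monthly minimum. As an illustration, assume a lognormal baseline (log-SD 0.6 to 1.0), about half the patients controlled, control more likely at lower baseline (log-odds 0.5 to 1.0 per SD), controlled patients skipping Months 3 and 9, and leaving unrelated to baseline. The record mean is then about 2 to 6% above the patient mean.
- Even with a given attrition pattern, the sign depends on which baseline is subtracted. In the hand example, subtracting 5.00 overstates the fall by 0.32 and subtracting 4.36 understates it by 0.32.

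**Conclusion.** The point holds in a limited form. The code does not request the quantity that the model is meant to assess, and it leaves the reference baseline to a default that the SAP does not state. If that default is the record mean, and if record count is related to baseline with a non-zero slope, all window means shift by one constant. Under the simulated assumptions the shift is 0.07 to 0.22 baseline SD where leaving depends on baseline, and about zero where it does not. Neither direction nor size in this study can be determined from the documents.

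Two stronger conclusions should not be drawn: that a model-based change is unobtainable, and that the time course is distorted. The first fails because level and change are the same fit, the second because the shift is constant over windows. Because the analysis is secondary and exploratory, this is an improvement at almost no cost, not a threat to a study conclusion.

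**What to change.** Make both changes together in SAP 6.2.3:
1. Model absolute change from baseline, `chg = window base`.
2. Fix the reference, `lsmeans window / at base=<constant> cl`, where the constant is the mean of one baseline value per patient among the FAS patients who enter the main model. Compute it once for each variable and each group analysed.

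Report LS mean change with its 95% interval for each window, state the constant in the table footnote, and use the same constant in both sensitivity analyses. The first change alone is not enough, because the (slope − 1) error remains.

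The cost is two edited statements and one computed number per model. The only decision is which patients define the constant, settled above. In the complete-case analysis the constant may lie away from that subset's own mean baseline, so its LS means rely somewhat more on the linear slope; a footnote giving both means covers this. Percentage change stays with the descriptive tables.

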#### 6.2.4 Confidence intervals for occurrence rates of AEs and SAEs

The occurrences of AE or SAE by preferred term will be modeled to follow approximately a Poisson process with constant intensity  $\theta$ . The rate parameter  $\theta$  will be estimated as  $\lambda=D/T$ , where

- Numerator ( $D_i$ ) = total number of events (AE or SAEs by PT) observed within the cohorts and overall ( $i=1,2,3$  for cohort 1, 2 and overall, respectively). PTs which were reported more than once on the same day (within the same patient) will be counted as one event under the highest severity grade.
- Denominator ( $T_i$ ) = The sum of exposure time  $t$  across all patients in group  $i$  per 100 patient years. For a single patient the exposure time  $t$  is derived as:  $t = (\text{minimum date of (last dose + 28 days, last contact day, analysis cutoff day)} - \text{date of first dose during study} + 1) / 365.25$ . The sum of the exposure time of all patients in group  $i$  will be divided by 100 to obtain the exposure time per 100 patient years.
- Note: the analyses of safety and tolerability assessments will concentrate on the on-treatment period, defined to be the period from Day 1 to 28 days after last dose of pasireotide s.c. i.e. the exposure period for  $T_i$  is accordingly adjusted.

Conditionally on  $T$ , an exact  $100*(1-\alpha)\%$  confidence interval for a Poisson variable with parameter  $\theta*T$  and observed value  $D$  can be obtained based on (Garwood, 1936), from which an exact  $100*(1-\alpha)\%$  confidence interval for  $D/T$  will be derived as follows (Sahai, 1993; Ulm, 1990):

$$\text{Lower confidence limit } L = \frac{0.5c_{\alpha/2,2D}}{T} \quad (\text{in SAS: } (0.5*\text{cinv}(\alpha/2,2*D(i))/T(i))$$

$$\text{Upper confidence limit } U = \frac{0.5c_{1-\alpha/2,2D+2}}{T} \quad (\text{in SAS: } (0.5*\text{cinv}(1-\alpha/2, 2*D(i)+2)/T(i)) \text{ for } i=1,2,3 \text{ and } D(i) > 0 \text{ and } 0 \text{ otherwise,}$$

where  $c_{\alpha,k}$  is the  $\alpha$ th quantile of the Chi-square distribution with  $k$  degrees of freedom.

Garwood, F. 1936. Fiducial limits for the Poisson distribution. *Biometrika*. 28(3/4):437-442

Ulm, K. 1990. A simple method to calculate the confidence interval of a standardized mortality ratio. *American Journal of Epidemiology* 131(2):373-375.

Sahai, H. and Khurshid, A. (1993a). "Confidence intervals for the mean of a Poisson distribution: A review", *BiomtrcJ*, 35, 857-867.

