6.3 Treatments (pasireotide s.c., concomitant therapies)

The medication for this study is pasireotide s.c. Prescribing information on the pasireotide s.c. start and stop dates, dose, dose changes and reason for changes. The actual mean daily dose and duration of drug exposure while in the study will be summarized by descriptive statistics and corresponding listing will be presented. Incidence rates by person-time of exposure and incidence rates by person-time of observation with their corresponding 95% confidence interval will be reported.

Concomitant medications and significant non-drug therapies prior to and after enrolling into the study will be summarized by preferred term and ATC class of the WHO-Drug Reference List.

These analyses will be performed on the safety set.

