### **Occurrences of AEs and SAEs adjusted for exposure**

The exposure times by cohort is different, therefore, exposure adjusted occurrence rates will aid in the interpretation of differences in the occurrence of AEs/SAEs. Exposure adjusted occurrence rates will be presented (per 100 years of patient exposure), together with 95% confidence intervals. Summaries will be presented for treatment emergent AEs and SAEs.

Confidence intervals will be derived assuming a Poisson process for the occurrence of AEs (SAEs). See Section 5.4 for further details.

Summaries of exposure adjusted occurrence rates will be produced for AEs and SAEs by PT. Only AEs (SAEs) with more than 2 occurrences per preferred term will be displayed.

The analyses on occurrences of AEs and SAEs will be repeated by country.

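### The Poisson limits on total AE counts are too narrow for preferred terms that recur unevenly across patients; they are adequate for infrequent or once-per-patient terms

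*SAP*

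**What the plan says.** SAP 6.2.4 sets one constant rate for each PT, within each cohort and overall: "The occurrences of AE or SAE by preferred term will be modeled to follow approximately a Poisson process with constant intensity". The numerator D is the "total number of events (AE or SAEs by PT) observed within the cohorts and overall". The only within-patient rule is that "PTs which were reported more than once on the same day (within the same patient) will be counted as one event"; repeats on different days all count. The denominator T is pooled exposure in units of 100 patient-years. The limits are L = 0.5·χ²(α/2, 2D)/T and U = 0.5·χ²(1−α/2, 2D+2)/T, and the section calls the resulting interval for D/T exact.

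The exposure-adjusted part of SAP 8.4.1 repeats the assumption: "Confidence intervals will be derived assuming a Poisson process for the occurrence of AEs (SAEs"). It says exposure differs by cohort and that the adjusted rates will help in reading differences in AE/SAE occurrence. It repeats the analysis by country and sets a display rule: "Only AEs (SAEs) with more than 2 occurrences per preferred term will be displayed".

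Neither section plans an over-dispersion check, a robust or clustered variance, a negative-binomial model, a bootstrap or a first-event rate. Protocol 6.3 asks only that "Incidence rates by person-time of exposure and incidence rates by person-time of observation with their corresponding 95% confidence interval will be reported"; it fixes neither the numerator nor the interval method.

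**The concern.** The Garwood interval is exact when D is a Poisson count. When patients differ in their underlying rate and can contribute several events, D varies more than a Poisson count with the same mean. The planned interval cannot reflect this, because the number of patients behind D does not enter the formula: thirty events in thirty patients and thirty events in six patients get the same limits.

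Safety is the primary objective and SAP 8.4 specifies no other confidence interval. Limits that are too narrow overstate precision and can make two cohorts with the same true rate look different. The display rule counts occurrences, so three events in a single patient qualify for an interval. With 100 to 200 patients in about 35 countries, a country averages 100/35 ≈ 3 to 200/35 ≈ 6 patients, so one patient can determine a country rate.

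**Working it through.** **Inputs from the documents.** The formulas, D, T and the 95% level (SAP 6.2.4 and 8.4.1); 100 to 200 patients (SAP 8.1.2); follow-up of up to 3 years (SAP 4.1).

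**Assumptions, not in the documents.** PT-specific rates, the dropout pattern, and a gamma-distributed patient rate with mean 1 and variance k (k = 0 is the SAP's own model).

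**Step 1: the plan's own level.** With k = 0, N = 100 or 200 and rates of 5 to 100 per 100 patient-years, simulated coverage of the SAP interval is 95.0% to 96.5%. The formula keeps its stated level when its assumption is true.

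**Step 2: one count, several spreads.** Take D = 30 in 200 patient-years (T = 2), N = 100, two years each.
- Rate: 30/2 = 15.0 per 100 patient-years.
- Garwood: L = 0.5 × 40.48/2 = 10.1; U = 0.5 × 85.65/2 = 21.4, however the events are spread.
- Patient-clustered, on the log scale: SE = √[(Σy² − D²/N)·N/(N−1)]/D, where y is events per patient; limits 15.0·exp(±1.96·SE).
- Example, ten patients with three events each: Σy² = 90 and D²/N = 9, so SE = √(81 × 100/99)/30 = 0.30 and the limits are 8.3 to 27.1.

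| Spread of the 30 events | Clustered 95% limits | Width relative to Garwood |
|---|---|---|
| 30 patients × 1 | 11.1 to 20.3 | 0.81 |
| 15 × 2 | 9.4 to 24.0 | 1.29 |
| 10 × 3 | 8.3 to 27.1 | 1.66 |
| 6 × 5 | 6.9 to 32.7 | 2.29 |

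With one event per patient, Garwood is not too narrow.

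**Step 3: coverage under between-patient variation.** Let φ = Var(D)/E(D). Then φ = 1 + kλ·E[t²]/E[t], and coverage is roughly 2Φ(1.96/√φ) − 1: about 89% at φ = 1.5, 83% at φ = 2 and 74% at φ = 3. With dropout of 0.5 per year capped at 3 years:
- E[t] = (1 − e^−1.5)/0.5 = 1.55 years
- E[t²] = 8(1 − 2.5e^−1.5) = 3.54
- E[t²]/E[t] = 2.28

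At λ = 0.5 and k = 1, φ = 1 + 0.5 × 2.28 = 2.14, which implies about 82%; simulation gives 84%. Simulated Garwood coverage at N = 100 (6,000 runs per cell):

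| Rate per 100 patient-years | k = 0.5 | k = 1 | k = 2 | k = 4 |
|---|---|---|---|---|
| 5 | 97% | 96% | 94% | 92% |
| 20 | 93% | 91% | 87% | 78% |
| 50 | 89% | 84% | 73% | 62% |
| 100 | 83% | 75% | 61% | 47% |

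N = 200 gives nearly the same figures, so more patients do not cure it. The clustered interval covers 92% to 96% throughout.

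A second exposure pattern (N = 150; exponential with mean 1.5 years, capped at 3 years, plus 28 days; mean about 1.4 years) gives, for k = 1, 2 and 4:
- 0.3 per patient-year: 90%, 83% and 73%
- 0.8 per patient-year: 78%, 66% and 53%
- clustered interval in these settings: 93% to 95%

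**Step 4: cohort comparison.** Two cohorts of 75 with identical true rates have non-overlapping Garwood intervals in 0.3% to 0.5% of runs when k = 0. At 0.3 and 0.8 per patient-year respectively, this rises to 2% and 8% for k = 1, and to 5% and 16% for k = 2.

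**Step 5: where the alternative is worse.** For a rare term in a small cohort (N = 60, 0.02 per patient-year, k = 0 to 2), among runs that pass the display rule, the clustered log-rate interval covers only 81% to 86%, against 90% to 95% for Garwood.

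**The case against.** The strongest reply is that these rates are descriptive and their assumption is disclosed. The SAP calls the process only approximately Poisson, no hypothesis test or rate ratio is planned, and patient counts by PT and cohort are tabulated separately. This stands as a limit on severity. It does not justify limits labelled exact with no check or fallback, on rates meant to help in comparing cohorts.

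A second reply is that recurrence is assumed. This stands in part. The Protocol introduction lists diarrhoea, nausea and hyperglycaemia as the most frequent AEs, but not as recurring in the same patients. Protocol 3.5.2.6 links the degree of hyperglycaemia to diabetic status, not the number of episodes. Protocol 3.5.2.1 follows an AE to resolution or permanence, so a persistent condition would be one event. On the other hand, SAP 8.4.1 has a rule for patients with multiple occurrences of an AE, and SAP 6.2.4 itself merges same-day repeats, so the plan does expect repeats.

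A reader might infer more than the documents support:
- *SAE rates are equally affected.* Protocol 3.5.2.2 and 7.1.1.2 have SAE re-occurrences reported as follow-ups to the original event. That governs the SAE form, and the eCRF could still hold separate entries, but it weakens the extension to SAEs.
- *The primary result is compromised.* The primary endpoint is a patient-level percentage and uses no Poisson interval.
- *The Protocol's incidence rates require one event per patient.* Protocol 6.3 defines no numerator, and that is a question of estimand, not of interval width.
- *Garwood should be replaced everywhere.* Step 5 of the working shows that this would harm rare terms.

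**Conclusion.** The concern holds for PTs that recur unevenly across patients, mainly frequent non-serious AEs. There the limits are too narrow by a factor of about √φ: 1.22, 1.41 and 1.73 for φ = 1.5, 2 and 3. Coverage of about 53% to 90% rests on assumed rates of 0.3 to 0.8 per patient-year, k from 1 to 4 and an assumed exposure pattern; none of these can be set from the documents. At 5 per 100 patient-years coverage is 92% to 97%, and for terms occurring at most once per patient the planned interval is adequate or slightly conservative. D/T does not change. Severity is moderate: the study is exploratory and the primary percentage is untouched, but these are the only safety intervals and they bear on cohort comparison.

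**What to change.** In SAP 6.2.4 and 8.4.1:

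1. Keep D/T, and show the number of patients contributing events beside D.
2. For terms with repeat events and at least a pre-specified number of contributing patients, replace the Garwood limits with a patient-clustered interval (Poisson regression with log exposure offset and patient-level robust variance), a negative-binomial interval or a bootstrap that resamples patients. Name one method and the threshold before database lock.
3. Keep Garwood for terms with at most one event per patient, or for a first-event rate: patients with an event divided by person-time to first event.
4. Where repeats come from very few patients, as is likely in country tables, show counts and rates without limits.
5. Drop the word exact for total-event rates.

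The cost is SAP wording and a few lines of SAS on data already collected. The downsides are wider intervals for frequent recurrent terms, and clustered intervals that are unstable when few patients contribute, which is why the threshold is needed.
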